Many chemotherapeutic agents compromise the integrity of the mucosal barrier in the gut, allowing translocation of gram-positive bacteria in secondary lymphoid organs. While this has, until recently, been considered an undesirable side-effect, it may also represent one mechanism by which chemotherapy stimulates an effective anti-cancer immune response. It has been proposed that the priming of Th17 T-cell responses against commensal microbes following disturbance of the gut mucosal barrier facilitates the accumulation of Th1 helper T cells at the site of the tumor, and thus contributes to tumor regression. Gut microbes may also contribute to the efficacy of chemotherapeutic agents through metabolism of the chemotherapeutic agent to its active form. We will test the hypothesis that gut microbial composition can influence immune response to the tumor, resulting in inter-individual differences in the response to anti-cancer therapies. We will also explore how host factors and microenvironmental factors influence the local immune response to the tumor.

We propose the following specific aims:

- 1. To demonstrate feasibility and acceptability of protocol procedures and measures, including in-home collection of a fecal sample, collection of a blood sample by venipuncture, and collection of breast tissue from newly diagnosed breast cancer patients prior to initiation of neoadjuvant breast cancer therapy.
- 2. To estimate rates of gastrointestinal side effects and pathological complete response in women with breast cancer treated with neoadjuvant chemotherapies, by breast cancer subtypes, tumor characteristics, cancer treatment, and by categorical measures of gut microbial composition, diversity, and metabolic activity.
- 3. To estimate the associations of pre-treatment gut microbial composition, diversity, and metabolic activity with anticancer immune responses, measured as relative abundance of immune infiltrates in pre-treatment FFPE breast tumor tissues, and as relative abundance of circulating lymphocytic subtypes (Th1, Th2, Th17, and Treg) in blood samples collected prior to initiation and following completion of neoadjuvant

IRB # 204897 Site: UAMS Version 5 06/07/2019

chemotherapy.

4. To estimate associations of local and systemic immune responses with host factors such as age, BMI, and smoking status, and with measures of the breast microenvironment including mammographic density and benign parenchymal enhancement on breast MRI.

Study Population

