We anticipate identification of 60 eligible women among patients diagnosed with breast cancer at UAMS and recommended for neoadjuvant therapy over the course of a year and estimate that, of these, 40 will consent to participate and complete study assessments.

Potentially eligible participants will be identified by their treating oncologist in the Medical Oncology Clinic. The study will be presented to potential participants prior to initiation of chemotherapy. We will allow the patient as much time as she needs to think about participation, and discuss her concerns with friends, relatives, and professional staff before making a decision.

Written consent will be requested from patients who meet eligibility criteria. The informed consent process will be conducted by study staff. We will not advertise for study participants. No compensation will be provided to study participants.

Inclusion Criteria

Eligible participants are women aged 18 years or older, who are:

- Diagnosed with invasive breast cancer and prescribed a regimen that includes neoadjuvant therapy prior to breast surgery.
- Able to provide informed consent.

Exclusion Criteria

- History of any previous malignancy, other than non-melanoma skin cancers
- Inability to tolerate phlebotomy
- Immunosuppressive therapy for any other condition
- Fever or active uncontrolled infection in the last 4 weeks
- Inflammatory bowel disease
- Surgery of the stomach, small or large intestines, appendectomy, gastric bypass or gastric banding in the past 6 months.
- Active autoimmune disease, including, but not limited to, SLE, MS, ankylosing spondylitis

Study Design

We propose a small longitudinal study to demonstrate the feasibility of measuring the gut microbiome and immune infiltrates in pre-treatment tumor tissue from newly diagnosed breast cancer patients who will subsequently undergo neoadjuvant therapies. This study will provide preliminary data in support of a proposal for an outcomes study of the roles of the gut microbiome in response to cancer therapies.

IRB # 204897 Site: UAMS Version 5 06/07/2019

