Fecal collection: The first fecal sample should be collected prior to initiation of neoadjuvant therapy; a second fecal collection will be collected after chemotherapy and prior to surgery. In each case, the sample will be collected by the participant at home using an OMNIgene GUT sample collection kit. The samples, labeled with a code and no other patient identifiers, can be brought to the clinic or can be mailed by participants to University of Arkansas for Medical Sciences, Cancer Clinical Trials Office, Re: IRB # 204897, [name]. If mailed, the postage date must be on or before the first day of chemotherapy treatment to be considered eligible to continue. It is vital that the first fecal sample be collected prior to the first dose of chemotherapy. Following receipt, samples will be aliquoted into cryovials and stored in a -80 C freezer in the [name] lab, until the complete batch can be sent to [name], c/o [name] / [name], at the Institute for Genome Sciences, University of Maryland School of Medicine, BioPark - 6th floor, [name]. Samples will be labeled with a unique code and no other identifiers prior to sending to the University of Maryland.

DNA extraction and sequencing: DNA will be extracted from fecal samples at the [name] lab. Microbial 16S rRNA genes will be amplified using indexed primers and sequenced using 454-pyrosequencing, as described in the paper by Fuhrman et al 2013 [29]. The DNA analysis that will be performed will focus on the identification and study of microbes in the sample rather than characterization of human genes.

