The Principal Investigator will carefully monitor study procedures to protect the safety of research subjects, the quality of the data and the integrity of the study. All study subject material will be assigned a unique identifying code or number. Data obtained during the study will be entered into C3PR and OpenClinica located in the UAMS clinical trial management suite. C3PR is a cancer Biomedical Informatics Grid (caBIG®, NCI) application that will keep a list of subjects

IRB # 204897 Site: UAMS Version 5 06/07/2019

enrolled and specific information regarding their enrollment. Data will be entered into OpenClinica through electronic web-based case report forms (CRFs). OpenClinica is a secure open source system for electronic data capture and clinical data management. Data from OpenClinica can be easily extracted for analysis throughout the study.

After informed consent is obtained, the data will be collected, coded with a study ID number, and stored indefinitely.

Data Analysis

Analyses will be conducted according to study aims. As the aims are considered exploratory, P values < 0.05 will be considered statistically significant and no adjustments will be made for multiple comparisons.

Aim 1. To assess the acceptability and feasibility of study procedures.

We will describe numbers and characteristics of women who are 1) screened, 2) eligible, 3) consented, and 4) complete collections for each type of biospecimen. In a brief form which will accompany the fecal sample, we will ask enrolled women specifically about the acceptability of, and logistical difficulties with, the procedures for collection and packaging of the fecal specimen.

Aim 2. To estimate proportions of patients with pathological complete response by host factors, breast cancer subtypes, tumor characteristics, reported gastrointestinal symptoms, and by categorical measures of gut microbial composition, diversity, and metabolic activity.

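### Aim 1's form-based results on stool-collection acceptability come only from women who return a sample, so they are likely to overstate acceptability and miss barriers

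*Combined protocol and SAP*

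**What the plan says.** The first specific aim is "To demonstrate feasibility and acceptability of protocol procedures and measures, including in-home collection of a fecal sample", followed by the blood and breast tissue collections.

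The Data Analysis section gives Aim 1 two components. The first is descriptive: how many women are screened, are eligible, consent, and "complete collections for each type of biospecimen", together with their characteristics. The second is the form: "In a brief form which will accompany the fecal sample, we will ask enrolled women specifically about the acceptability of", with practical difficulties added, "the procedures for collection and packaging of the fecal specimen".

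The fecal collection text under Microbial DNA assays says that samples "can be brought to the clinic or can be mailed by participants". For the baseline sample it adds: "If mailed, the postage date must be on or before the first day of chemotherapy treatment to be considered eligible to continue". There are two collections per woman, since "a second fecal collection will be collected after chemotherapy and prior to surgery".

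The Schedule of Study Events lists a general questionnaire, the FACT-G7 and a gastrointestinal checklist. It lists no acceptability questionnaire. The section on withdrawal has no exit question and no item for the reason a sample is missing.

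**The concern.** The form is addressed to enrolled women, but it travels with the specimen. A woman who never produces a specimen has no described way of answering. The respondents are thus defined by having done the thing they are asked to judge.

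Women who found home collection unpleasant, confusing or impossible to fit in before treatment are the likeliest to be missing, so the answers will tend to look better than those of all consented women. The postmark rule adds to this: a woman with the practical problems that the form asks about may miss the window and leave the study unasked.

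The stated purpose of the pilot is to prepare a larger outcomes study. The larger study needs to know whether samples are lost because women object to the procedure, because the kit or mailing fails, or because chemotherapy starts too soon. Each calls for a different remedy, and a count of missing samples does not tell them apart.

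**Working it through.** **Is there a figure in the plan to reproduce?** No. The documents state no return rate, acceptability rate or acceptability target. The one Aim 1 precision statement (Power and Sample Size: 60 screened, plus or minus 20%) concerns willingness to participate, so it neither supports nor answers this point.

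**Who can be heard, on the text as written**

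| Group | In the completion counts? | Route to the form? |
|---|---|---|
| Consented, both samples returned | Yes | Yes |
| Consented, first sample only | Yes | Yes, for the first; nothing is asked about the missing second |
| Consented, no sample returned | Yes | None described |
| Consented, baseline sample mailed too late | Yes | Perhaps, if the form came with the late sample; no later contact is described |

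The text does not say whether the form goes with both samples or only one.

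**Size of the distortion.** Let r be the share of consented women who return a sample and the form, a1 the acceptability among them, and a0 the acceptability among the rest.

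- Form-based result: a1
- Result over all consented women: r × a1 + (1 − r) × a0
- Overstatement: a1 − [r × a1 + (1 − r) × a0] = (1 − r)(a1 − a0)

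It is zero if everyone returns a sample (r = 1) or if non-returners feel as returners do (a0 = a1). It would be negative if non-returners were more accepting.

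**Illustration at r = 0.80 and a1 = 0.90 (assumed)**

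- a0 = 0.90: 0.20 × (0.90 − 0.90) = 0 points
- a0 = 0.50: 0.20 × (0.90 − 0.50) = 8 points
- a0 = 0: 0.20 × (0.90 − 0) = 18 points

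**Sensitivity to the return rate**, with 40 women enrolled and about 90% of returners accepting, in whole women (all assumed):

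| Returned | Accepting | Form result | Over all 40, no non-returner accepts | Overstatement | Over all 40, half accept | Overstatement |
|---|---|---|---|---|---|---|
| 38 | 34 | 89.5% | 34/40 = 85.0% | 4.5 | 35/40 = 87.5% | 2.0 |
| 36 | 32 | 88.9% | 32/40 = 80.0% | 8.9 | 34/40 = 85.0% | 3.9 |
| 32 | 29 | 90.6% | 29/40 = 72.5% | 18.1 | 33/40 = 82.5% | 8.1 |
| 27 | 24 | 88.9% | 24/40 = 60.0% | 28.9 | 30.5/40 = 76.2% | 12.6 |

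The return rate and the views of non-returners drive the result. The plan does not give the first and does not collect the second.

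**The case against.** The best reply is that Aim 1 does not rest on the form. The plan counts and describes women at every stage from screening to completion, so non-returners stay in those denominators. Uptake and completion are themselves behavioural evidence of acceptability. A reader might infer that Aim 1 as a whole is biased upward; the documents do not support that. Only the answers on acceptability and practical difficulty are exposed.

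Other parts of the reply also stand:

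- **Direction.** The upward direction is inferred. Some samples will be missing for reasons unrelated to the procedure, such as too little time before the first treatment. It is not certain that the form will overstate acceptability.
- **Who is silent.** It is too strong to say that every woman who misses a sample goes unheard. One who returns the first and not the second can answer once.
- **Return of the form.** The text says that the form accompanies the sample. It does not expressly forbid returning it alone, though no such route is described.
- **Size.** A reader might combine the enrolment ceiling of 50 with the expected 40 and read off an 80% return rate. The Study Population section says only that, of 60 eligible, the investigators "estimate that, of these, 40 will consent to participate and complete study assessments". Consent and completion are not separated, so no return rate follows.
- **Weight.** No scale, threshold or go/no-go rule is attached to the form, and the aims are called exploratory.

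None of this gives a non-returner a way to answer. The counts show how many samples are missing and from whom, but not why.

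**Conclusion.** The point holds for the form-based part of Aim 1. Followed as written, the plan gives acceptability and practical-difficulty results from a group selected on having returned a sample, and these are likely to look too favourable. Completion counts, women's characteristics and the willingness-to-participate estimate are not affected, and neither are Aims 2 to 4.

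The size cannot be determined from the documents. It is (1 − r)(a1 − a0): 0 to 18 points at the assumed 80% return and 90% acceptability among returners, and about 29 points at most in the less favourable assumed case of 27 returned out of 40. These ranges assume that non-returners are no more accepting than returners. They show how far the result could move and do not predict what will be found.

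The change is worth making because acceptability is a stated aim of the pilot, and reasons for non-return are hard to recover reliably afterwards.

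**What to change.** 1. Offer the same short form, separately from the specimen, to every consented woman whose baseline or pre-surgery sample does not arrive. Do this at a routine visit or by phone. Participants already complete questionnaires at routine chemotherapy visits.
2. Record a brief, voluntary reason for each missing sample, so that objection to the procedure, kit or mailing problems, and lack of time before treatment can be told apart.
3. State whether the form goes with both collections. Report acceptability over all consented women, with those who did not answer shown as a separate category. Some will decline the form too, so this reduces the selection without removing it.

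The cost is one short contact per missing sample. If 32 of 40 returned a baseline sample, that would be 8 contacts. Some would be with women no longer eligible to continue under the postmark rule; the protocol describes no follow-up for them, so the contact would have to be written in and submitted to the IRB as a modification. No specimen or visit is added.

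Recording why eligible women decline before consent would also be useful, but it concerns a different group and is a separate, optional addition.

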We will estimate and compare rates of pCR by each factor using chi-squared tests for crude comparisons and multivariable logistic regression for adjusted comparisons. Factors of interest will include host factors such as age and menopausal status; and tumor characteristics including: intrinsic subtype assessed using clinically indicated measures (ER and PR status, Her2/neu status, and Ki67 positivity); standard clinical prognostic indicators (TNM stage and histologic grade), and subgroups defined using tertiles of all continuous gut microbial measures.

Aim 3. To estimate the associations of pre-treatment gut microbial composition, diversity, and metabolic activity with anticancer immune responses, measured as relative abundance of immune infiltrates in pre- treatment FFPE breast tumor tissues, and as relative abundance of circulating immune cell subtypes (Th1, Th2, Th17, and Treg) in baseline and longitudinal blood samples. Bivariate and covariate-adjusted associations among measures will be evaluated using Spearman's rank test and General Linear Models, respectively.

Aim 4. To estimate associations of the measures of local and systemic immune responses with host factors such as age, BMI, and smoking status, and with measures of the breast microenvironment including mammographic density and benign parenchymal enhancement on breast MRI. Bivariate and covariate-adjusted associations among measures will be evaluated using Spearman's rank test and General Linear Models, respectively.

Power and Sample Size:

Aim 1: If we screen 60 potential participants, we should be able to estimate, with 95%

IRB # 204897 Site: UAMS Version 5 06/07/2019

confidence, the true proportion of this patient population willing to participate in the study with precision of +/- 20%.

Aim 2: If 40 participants are enrolled and complete study measures, and the expected pCR in the category with the greatest risk of mortality is assumed to be 20%, then we will have 47% power to detect a statistically significant trend in rates of pCR across tertiles of microbiome measures if the odds ratio for the highest tertile is 5.0.

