Aim 3 and 4: If we have 20 participants with both tumor infiltrate measures and measures of gut microbial composition, we will have adequate power (β =80%) to detect relationships between the dependent variable (relative abundances of tumor infiltrating lymphocytes and circulating lymphocytes) and the independent variables gut microbial composition, diversity and metabolic activity; host factors, and measures of the tumor microenvironment) at a two-sided α =0.05 significance level, when the true change in the dependent variables is 0.67 standard deviations per one standard deviation change in the independent variables.

Ethical Considerations

This study will be conducted in accordance with all applicable government regulations and University of Arkansas for Medical Sciences research policies and procedures. This protocol and any amendments will be submitted and approved by the UAMS Institutional Review Board (IRB) to conduct the study. In addition, all study personnel must have completed human subject protection training.

The formal consent of each subject, using the IRB-approved consent form, will be obtained before that subject is submitted to any study procedure. All subjects for this study will be provided a consent form describing this study so they can make an informed decision about their participation in this study. The person obtaining consent will thoroughly explain each element of the document and outline the risks and benefits, alternate treatment(s), and requirements of the study.

The consent process will take place in a quiet and private room, and women may take as much time as needed to make a decision about their participation. The privacy of all subjects will be maintained and questions regarding participation will be answered. No coercion or undue influence will be used in the consent process. This consent form must be signed by the subject and the individual obtaining the consent. A copy of the signed consent will be given to the participant, and the informed consent process will be documented in each subject's medical record.

Dissemination of Data

Results of this study may be used for presentations, posters, or publications. The publications will not contain any identifiable information that could be linked to a participant.

References

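### Aim 2 states power for a trend in pCR across microbiome tertiles, but its analysis names no trend test or tertile score (minor, cheap to fix)

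*Combined protocol and SAP*

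**What the plan says.** Data Analysis, Aim 2, compares pCR rates by each factor "using chi-squared tests for crude comparisons and multivariable logistic regression for adjusted comparisons". The factors range from menopausal status, intrinsic subtype, stage and grade to "subgroups defined using tertiles of all continuous gut microbial measures". The section names no trend test. It also does not say whether tertile enters the logistic model as an ordered score or as two indicators.

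Power and Sample Size, Aim 2, takes 40 participants who complete study measures, says that "the expected pCR in the category with the greatest risk of mortality is assumed to be 20" percent, and claims "47% power to detect a statistically significant trend in rates of pCR across tertiles of microbiome measures". The effect size behind this claim is given by the condition "if the odds ratio for the highest tertile is 5.0". It does not give the middle-tertile rate, the comparator for the odds ratio, or whether the test is one- or two-sided.

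The opening of Data Analysis declares the aims exploratory and says "P values < 0.05 will be considered statistically significant and no adjustments will be made for multiple comparisons". A two-sided level is stated only for Aims 3 and 4 ("at a two-sided α =0.05 significance level").

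**The concern.** A trend test uses the order of the tertiles and spends one degree of freedom. An ordinary chi-squared test on a 3 x 2 table ignores the order and spends two. The plan states power for the first kind of question, while its analysis text, applied literally, leads to the second kind of test. An analyst who runs the same chi-squared procedure on every listed factor would then have less power than stated whenever pCR rises in steps across tertiles.

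The open choice also matters in itself. A 2-df test, a 1-df trend test and a highest-versus-lowest contrast can give different p-values on the same 40 patients. With many microbial measures and no multiplicity adjustment, it is better to fix the test before the data are seen.

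**Working it through.** **Inputs from the protocol.** N = 40; reference pCR 20%; odds ratio 5.0 for the highest tertile; significance at 0.05; stated power 47%.

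**Assumptions (not in the protocol).** The 20% belongs to the lowest tertile. The odds ratio is highest versus lowest. The test is two-sided. Tertiles are equal, n = 40/3 = 13.33. The middle rate p2 is varied from 20% to the highest-tertile rate.

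**Rates.** Lowest: p1 = 0.20, odds 0.25. Highest: odds 0.25 x 5 = 1.25, so p3 = 1.25/2.25 = 0.556. Log-linear middle: odds 0.25 x √5 = 0.559, so p2 = 0.559/1.559 = 0.359. Mean rate = (0.200 + 0.359 + 0.556)/3 = 0.371.

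**Step 1: reproduce the 47%.** Cochran-Armitage test with centred scores -1, 0, 1 (equivalent to 0, 1, 2):
- Expected statistic: n(p3 - p1) = 13.33 x 0.3556 = 4.741.
- Null variance: 2n x 0.371 x 0.629 = 6.225, SD 2.495.
- Variance under the alternative: n(0.20 x 0.80 + 0.556 x 0.444) = 5.426, SD 2.329.
- Power: Φ[(4.741 - 1.96 x 2.495)/2.329] = Φ(-0.064) = 47.4%.

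This matches the stated figure but does not prove which test was used. Comparing highest with lowest only, with 13.33 per group, has the same expected statistic (4.741). The pooled rate is 0.378, so the null SD is √(26.67 x 0.378 x 0.622) = 2.504. Power is Φ[(4.741 - 1.96 x 2.504)/2.329] = 47.2%.

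**Step 2: ordinary 2-df chi-squared test, same inputs.** Noncentrality = n Σ(p - 0.371)² / (0.371 x 0.629) = 3.62. Power against the 5% critical value on 2 df is 38.1%.

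**Step 3: vary the middle rate (large-sample formulas).**

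| Middle-tertile pCR | Trend, 1 df | Chi-squared, 2 df |
|---|---|---|
| 20% (equals lowest) | 50.4% | 51.9% |
| 30% | 48.4% | 40.9% |
| 35.9% (log-linear) | 47.4% | 38.1% |
| 45% | 46.2% | 38.8% |
| 55.6% (equals highest) | 45.2% | 46.6% |
| 65% (non-monotone) | 45% | 59% |

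Over all monotone middle rates, trend power is 45-50% and 2-df power 38-52%. The trend test leads for middle rates of about 21% to 54%. Its largest lead is 9.5 points, at 37.4%.

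**Step 4: check without the large-sample formula.** Full enumeration of outcomes, log-linear rates, with type I error at a common rate of 37%:

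| Split | Trend power | 2-df power | Trend type I error | 2-df type I error |
|---|---|---|---|---|
| 13/13/14 | 48.9% | 39.2% | 0.050 | 0.051 |
| 13/14/13 | 53.3% | 37.0% | 0.066 | 0.051 |
| 14/13/13 | 49.9% | 39.5% | 0.050 | 0.051 |

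The gap is not an artefact of the approximation. At 13/14/13 part of the 16.3 points (53.3 - 37.0) comes from the trend test's type I error of 0.066.

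**Step 5: logistic model.** Likelihood-ratio tests in the unadjusted model, same pattern and splits: 49-53% power with an ordinal score, 41-42% with two tertile indicators. The coding of tertile therefore matters in the regression too.

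**The case against.** The strongest reply is that the plan, read as a whole, already signals a trend analysis. The term chi-squared test can cover a 1-df test for trend, logistic regression can take an ordinal score, and the power paragraph names a trend. The 47% reproduces under that reading. This stands. A reader might infer that the protocol commits to a 2-df test, or that 47% is wrong; the documents support neither. What remains is that the analysis text never names the test whose power is given.

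Second, little depends on the figure. The protocol describes a pilot meant to show feasibility and estimate parameters. Under Study Population, the 40 is the number expected to consent and complete assessments out of 60 eligible women, so it is not derived from this power calculation. Tertile-specific pCR rates are the same whichever test is used, and 47% is already low. This also stands, and it keeps the point minor.

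Third, the trend test is not uniformly better. By the large-sample formula, the 2-df test is marginally ahead at both ends of the monotone range, and about 14 points ahead (59% against 45%) with a middle rate of 65%. Apart from the power sentence, the documents state no monotone hypothesis for the microbial measures. That is a genuine cost of the proposed change. The answer to it is that a trend is the effect the plan itself chose to power.

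**Conclusion.** The point holds as a minor mismatch. Power is stated for a trend, and the analysis does not name a trend test or an ordinal score. If tertiles are tested with the ordinary 2-df chi-squared test, power is about 38% (37-40% by enumeration), against 47% (49-53% by enumeration) for the trend test. These figures assume 20% in the lowest tertile, an odds ratio of 5.0 for highest versus lowest, two-sided 0.05, near-equal tertiles and a log-linear middle rate.

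The size depends on the middle rate, which the protocol does not give. The limits of 9.5 points at most, and about nil when the middle tertile equals the lowest or highest, are large-sample results. At 13/14/13 enumeration still puts the trend test ahead at both ends (54.3% against 51.3%, and 53.0% against 47.4%), partly through its inflated type I error. A reader might take the 16.3-point gap at 13/14/13 as the true loss; for the same reason it should not be read that way.

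Nor do the documents support the inference that the study's size or any decision is undermined: the aims are exploratory, and no sample size or decision rule uses the 47%.

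**What to change.** In Data Analysis, Aim 2, add one or two sentences, for example: *For tertiles of gut microbial measures, pCR will be compared with a two-sided 1-df Cochran-Armitage trend test (crude) and with tertile entered as an ordinal score 0/1/2 in the logistic model (adjusted). Unordered factors will be compared with ordinary chi-squared tests. pCR rates will be reported for each tertile.*

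If the 2-df test is what is intended, keep it and restate Aim 2 power as about 38-52% for monotone patterns, lowest for a graded effect, with the assumed middle rate.

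In either case it would help to record the power inputs: the comparator for the odds ratio, the tertile with the 20%, the middle rate and the sidedness. That is documentation only, since the natural reading already reproduces the 47%.

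Cost: no new data or patients. The trend test loses power for non-monotone patterns (about 45% against 59% with the middle tertile at 65%), and its type I error reaches 0.066 at the 13/14/13 split. The tertile-specific rates would still show a non-monotone or threshold shape.
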